Phendimetrazine (PHEN), a Schedule III medication under the Controlled Substance Act, is indicated for treating obesity. After oral administration, PHEN is converted to phenmetrazine, which is largely responsible for its behavioral and neuropharmacological effects. Consistent with the notion that compounds with intermediate 5-HT/DA release ratios selectively attenuate the reinforcing effects of COC, phenmetrazine (5-HT/DA ratio = 37) completely eliminated COC-maintained responding in monkeys. Recent research with PHEN has also shown that the parent compound reduces COC self-administration. Moreover, PHEN does not maintain self-administration and produces only limited positive subjective effects compared to d-amphetamine in COC users, which suggests that its abuse potential is low. Although PHEN has yet to be tested as a potential pharmacotherapy for COC dependence in human laboratory experiments or clinical trials to our knowledge, the results of extant preclinical experiments suggest it is a viable option.

In an ongoing study, we have demonstrated that COC can be safely administered to patients maintained on 70, 140 and 210 mg PHEN/day. Whether PHEN attenuates the reinforcing effects of COC, the best predictor for treatment efficacy (Comer et al., 2008; Haney and Spearman, 2008), remains to be determined. **The specific aim of this study is to demonstrate that PHEN maintenance reduces the reinforcing effects of intranasal COC.** To accomplish this aim, we will conduct an experiment in which non-treatment seeking COC-using participants (N=36) will be maintained on doses of PHEN (0 and 210 mg/day [target dose, dose will be titrated up as described below]). The reinforcing and other behavioral effects of intranasal COC (0 [placebo], 20, 40 and 80 mg) will be determined after 7 days of maintenance on the target PHEN dose (i.e., 210 mg/day). In order to monitor the safety of the drug combinations, cardiovascular measures will be taken routinely throughout experimental sessions and subjects will complete a daily side effect scale with nursing staff. We hypothesize that PHEN will attenuate the reinforcing effects of COC, as well as other abuse-related effects of COC (i.e., positive subjective effects). We also hypothesize that COC will be well tolerated during active PHEN maintenance.

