Progressive-ratio data (i.e., break point, number of COC doses earned) will be analyzed with two-factor mixed-model ANOVA with COC (within-subject variable; 0 [placebo], 20, 40 and 80 mg), and PHEN (within-subject variable; 0 and 210 mg/day) as the factors. A significant attenuation (i.e., rightward shift in the dose response) of the effects of COC will be inferred if the main effect of PHEN or the interaction of COC and PHEN attains statistical significance in the ANOVA. If the COC-PHEN interaction attains statistical significance, the mean square error term will be used to conduct Tukey's HSD *post-hoc* test to make appropriate pair-wise comparisons between means. Peak-effect and AUC data for the cardiovascular, performance and subjective effects measures obtained during the sampling phase will be analyzed in a similar fashion. Cardiovascular, performance and subjective effects data from the self-administration phase will not be analyzed because participants will likely ingest varying amounts of COC making these data difficult to interpret.

The primary outcome measures for this study are the break point and number of COC doses earned on the progressive-ratio procedure in subjects maintained on active PHEN or placebo. Considering the complete within-subject design, number of dose levels of each drug (i.e., two PHEN conditions and four doses of intranasal COC) enrolling 36 subjects will provide adequate power to detect an effect size ( $d$ ) of at least 0.44 for attenuation of the reinforcing effects of COC as a function of maintenance on PHEN and placebo ( $\text{power} = 0.80$ ,  $\alpha = 0.05$ , G\*Power). We used the results of a previous study conducted in our laboratory to determine an appropriate sample size for the present experiment ([name] et al., 2010). That study demonstrated that d-amphetamine maintenance decreased the reinforcing effects of COC with an estimated effect size ( $d$ ) of approximately 0.46.

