## **17. DATA AND SAFETY MONITORING**

### *Data Monitoring Plan*

Data will be collected using a computerized data collection and management system wherever possible. This system automates the collection of data, which ensures the accuracy and completeness of data collection. The data are stored in a unique file on the hard drive of the computer and are printed after all the tasks are completed. In all instances, the data files do not contain the name of the subject, but instead, each subject is identified by a unique four-digit number. A computer file linking the unique number with the subject's name will be kept on a stand-alone, password-protected computer. All data requiring hand entry (e.g., cardiovascular measures) will be entered by two separate staff members and comparison macros will be run to ensure accuracy. Data files for experimental tasks and physiological measures from each experimental session will be manipulated and combined into a single electronic spreadsheet for each subject by one of the investigators. Data for all subjects will then be combined into a single electronic spreadsheet and separated by experimental measure for statistical analysis using SPSS (IBM, Armonk, NY).

In this protocol the primary outcome measure will be the influence of PHEN maintenance on the reinforcing effects of COC. The alpha level will be set at 5%.

As noted above, wherever possible, data are collected using an automated computer system, which increases the accuracy and completeness of data collection and ensures the validity and integrity of the data. The initial data manipulation described above will be conducted twice and compared. The quality of manipulated data and data analyses will be monitored by random inspection by the PI and/or Co-Investigators.

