## **APPENDIX A**

### **Subjective Drug-Effect Questionnaires Descriptions**

*Adjectives Rating Scale (ARS)*

**Individual questions are presented sequentially, one at a time. Subjects rate their response to each question on a 5-point scale (0 = Not at all, 1 = A little, 2 = Moderately, 3 = Quite a bit, 4 = Extremely).**

(1) How "**ACTIVE**" do you feel right now? (2) How "**AGITATED**" do you feel right now? (3) How "**CLUMSY**" do you feel right now? (4) How "**ALERT**" do you feel right now? (5) How "**DIZZY**" do you feel right now? (6) How "**CONFUSED**" do you feel right now? (7) How "**ENERGETIC**" do you feel right now? (8) Are you in a "**GOOD MOOD**" right now? (9) How "**DAZED**" do you feel right now? (10) How "**EXCITED**" do you feel right now? (11) How "**SLEEPY**" do you feel right now? (12) How "**DEPRESSED**" do you feel right now? (13) How "**EUPHORIC**" do you feel right now? (14) Are you experiencing an "**IRREGULAR HEARTBEAT**" right now? (15) Do you feel as if you would have "**DIFFICULTY WALKING**" right now? (16) How "**TALKATIVE**" do you feel right now? (17) Are your "**MUSCLES TWITCHING**" right now? (18) How "**DROWSY**" do you feel right now? (19) How "**NAUSEOUS**" do you feel right now? (20) How "**DRUNK**" do you feel right now? (21) How "**NERVOUS**" do you feel right now? (22) How "**FATIGUED**" do you feel right now? (23) Is your "**HEART RACING**" right now? (24) How "**IRRITABLE**" do you feel right now? (25) How "**RESTLESS**" do you feel right now? (26) How "**LAZY**" do you feel right now? (27) How "**SHAKY**" do you feel right now? (28) How "**RELAXED**" do you feel right now? (29) How "**TIRED**" do you feel right now? (30) How "**SLUGGISH**" do you feel right now? (31) How "**SWEATY**" are you right now? (32) How "**SPACED OUT**" do you feel right now?

*Drug Effect-Questionnaire (DEQ)-VAS*

**Individual questions are presented sequentially, one at a time. Subjects rate their response to each question by marking a 100-unit line anchored with "Not at All" on the left side and "Extremely" on the right side.**

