(1) Is the drug producing "**ANY EFFECT**" right now? (2) Is the drug producing any "**BAD EFFECTS**" right now? (3) Is the drug producing any "**GOOD EFFECTS**" right now? (4) Is the drug making you feel "**HIGH**" right now? (5) Are you experiencing a "**RUSH**" from the drug right now? (6) How much do you "**LIKE**" the drug right now? (7) Is the drug making you feel "**STIMULATED**" right now? (8) Is the drug "**IMPAIRING YOUR PERFORMANCE**" right now? (9) Is the drug "**IMPROVING YOUR PERFORMANCE**" right now? (10) Based on how the drug effect feels right now, would you be willing to "**TAKE THIS DRUG AGAIN**"? (11) Based on how the drug effect feels right now, would you be willing to "**PAY FOR THIS DRUG**"? (12) Is the drug making you feel "**ACTIVE, ALERT OR ENERGETIC**" right now? (13) Is the drug making you feel "**EUPHORIC**" right now? (14) Is the drug making you experience an "**IRREGULAR OR RACING HEARTBEAT**" right now? (15) Is the drug making you "**TALKATIVE OR FRIENDLY**" right now? (16) Is the drug making you feel "**NAUSEATED, QUEAZY OR SICK TO YOUR STOMACH**" right now? (17) Is the drug making you feel "**SHAKY OR JITTERY**" right now? (18) Is the drug making you feel "**NERVOUS OR ANXIOUS**" right now? (19) Is the drug making you feel "**RESTLESS**" right now? (20) Is the drug making you feel "**SLUGGISH, FATIGUED OR LAZY**" right now?

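### No item or summary is named to carry the secondary hypothesis of reduced positive subjective effects, so the unadjusted either-test rule gives it a false-claim rate well above 5%

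*Combined protocol and SAP*

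**What the plan says.** Section 1 (Background) states a hypothesis beyond reinforcement: that PHEN will also attenuate "other abuse-related effects of COC (i.e., positive subjective effects". It does not say which measures represent those effects.

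Section 7 (Data Analysis) describes a two-factor within-subject ANOVA for the progressive-ratio data. Attenuation "will be inferred if the main effect of PHEN or the interaction of COC and PHEN attains statistical significance in the ANOVA". The next outcomes follow in the same paragraph: "Peak-effect and AUC data for the cardiovascular, performance and subjective effects measures obtained during the sampling phase" "will be analyzed in a similar fashion".

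Section 7 sets significance at p ≤ 0.05, and section 17 (Data Monitoring Plan) repeats it: "The alpha level will be set at 5" per cent. Neither place divides alpha across measures, between peak and AUC, or between the two ANOVA tests. Tukey's HSD is the only multiplicity control. It compares cell means within one outcome after a significant interaction.

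Appendix A lists 32 adjective-rating (ARS) items and 20 drug-effect (DEQ) items. "Individual questions are presented sequentially, one at a time", and no subscale, total or composite score is defined for either questionnaire.

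**The concern.** A stated hypothesis needs a rule that says which result would support it. Here the rule is permissive in four ways at once: many items, two summaries of each, two qualifying tests per ANOVA, and no sign attached to either test. Tukey's HSD does not help, because it works inside one outcome and does not gate a claim that rests on the PHEN main effect.

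A finding that PHEN reduces liking or high would naturally be cited beside the reinforcement result as evidence for the drug. If it came from one or two significant items among many, a reader could not tell it from chance.

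**Working it through.** **The plan's own figure.** The documents give no family-wise error rate for the sampling measures. The only operating characteristic is power of 0.80 for d = 0.44 with N = 36, and it concerns reinforcement. A paired t-test with d as the standardised difference gives 0.83 one-sided and 0.73 two-sided. That figure does not bear on this point.

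**Inputs from the documents**
- Per-test alpha 0.05; N = 36, fully within-subject (section 7).
- Two summaries per measure and two qualifying tests per ANOVA (section 7).
- Four COC doses, so the interaction has 3 degrees of freedom.

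**Inputs assumed**
- Positive-effect items. A broad classification takes 11 DEQ items (good effects, high, rush, like, stimulated, improving performance, take again, pay for, active/alert/energetic, euphoric, talkative/friendly) and 7 ARS items (active, alert, energetic, good mood, excited, euphoric, talkative): 11 + 7 = 18. A narrower set of 10 is used as the other end.
- Inter-item correlation 0.3 to 0.7; peak-AUC correlation within an item 0.8. The documents give no correlations.

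**Step 1: one ANOVA.** The chance that at least one of two independent tests is significant under no PHEN effect is 1 − 0.95² = 0.0975.

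**Step 2: expected false attenuations.**
- 18 items: 18 × 2 = 36 ANOVAs; 36 × 0.0975 = 3.5.
- 10 items: 10 × 2 = 20 ANOVAs; 20 × 0.0975 = 1.95.

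**Step 3: upper reference, all tests independent.**
- 18 items: 72 tests, 1 − 0.95^72 = 0.975.
- 10 items: 40 tests, 1 − 0.95^40 = 0.871.
- Main-effect decrease only (0.025 per ANOVA): 1 − 0.975^36 = 0.598 and 1 − 0.975^20 = 0.397.

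**Step 4: correlated items.** Simulated with no PHEN effect, N = 36, normal data, a 2 × 4 within-subject ANOVA and 5,000 runs (simulation standard error at most 0.007). The entries are the chance of at least one false attenuation.

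| Items | Inter-item correlation | Either test, any direction | Main-effect decrease only |
|---|---|---|---|
| 10 | 0.3 | 0.75 | 0.26 |
| 10 | 0.5 | 0.66 | 0.20 |
| 10 | 0.7 | 0.51 | 0.15 |
| 18 | 0.3 | 0.90 | 0.37 |
| 18 | 0.5 | 0.79 | 0.28 |
| 18 | 0.7 | 0.61 | 0.18 |

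Variants of the simulation put the lowest literal-rule entry between 0.50 and 0.54. For 10 items, if interactions whose average PHEN effect is a decrease also count alongside main-effect decreases, the chance is 0.31 to 0.47.

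**Step 5: after the fix.** With, for illustration, five named items, one summary and one contrast each, Holm's first step is 0.05/5 = 0.01. The family-wise error is then at most 5 × 0.01 = 0.05, whatever the correlations.

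**The case against.** **These are not primary outcomes.** Section 7 names break point and doses earned as primary, and section 2 includes the battery to characterise PHEN more fully. Unadjusted secondary analysis is defensible in a 36-person laboratory study. This stands as a reason to rate the point low. It does not remove it, because section 1 states the hypothesis and nothing labels these analyses exploratory.

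**Similar fashion may carry over only the ANOVA and Tukey test.** The documents do not spell out that the attenuation rule comes with them. Carrying it over is the natural reading, since the rule sits in the same paragraph. On the narrower reading, the hypothesis has no decision rule at all, and the same edit repairs that.

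**Direction would be respected in practice.** Section 7 glosses attenuation as a rightward shift, and nobody would report increased liking as attenuation. That is fair and lowers the figures considerably, which is why both columns are shown. The trigger itself states no sign, and even the directional figures are about three to seven times nominal.

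**A stronger reading is tempting.** Counting 32 ARS items, 20 DEQ items, 2 DSST scores and 4 vital signs gives 58 measures, 58 × 2 × 2 = 232 tests and 232 × 0.05 = 11.6 expected false positives. A reader might infer that false support is close to certain. The documents do not support that for this hypothesis: clumsiness, nausea, bad effects, psychomotor scores and blood pressure cannot show reduced positive effects. Nor do they say that one significant item confirms the hypothesis. The gap is that they do not say how many, or which, would.

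**Conclusion.** The point holds as a minor weakness in a secondary hypothesis. For 10 to 18 positive-effect items, the chance of at least one false attenuation is roughly 50% to 90% under the rule as written and about 15% to 37% if only a significant main-effect decrease counts, against 5%.

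These figures rest on my classification of items, the assumed correlations, normal data (the ARS items are 5-point ratings), items being analysed singly, and the attenuation rule applying to the sampling measures. The conclusion is that false support is plausible to likely, not that it is near certain. The primary progressive-ratio conclusions do not depend on this family and are unaffected.

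**What to change.** Before unblinding, add a short paragraph to Data Analysis in section 7 that:

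1. Names a short family of positive-effect items for the section 1 hypothesis.
2. Names one summary, peak or AUC. Which items and which summary are the investigators' choice, since the two summaries capture different features of the effect.
3. Tests each item with one prespecified contrast for a reduction in the COC effect under PHEN, in place of the either-test rule.
4. Applies Holm across the family at 5%.
5. Reports the other items and the other summary as exploratory, with no inference of attenuation.

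No subjects, sessions or measures are added. Results outside the family can no longer support the claim on their own, and power per item falls. In a five-item family at d = 0.44 (borrowed from the primary outcome as a benchmark), a two-sided paired test has power 0.73 at 0.05 and 0.48 at Holm's first step of 0.01. Holm relaxes after each rejection, so the loss is smaller when several items move together. A short family keeps it down.

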## **4. STUDY POPULATION**

Up to 100 individuals will be screened to participate in this study. We intend to enroll thirty six (24 male and 12 female) completers into the study. These individuals must be English-speaking, English-reading subjects 18-55 years of age of varying ethnic backgrounds and they will be recruited to participate in this five-week experiment. Enrollment in this study will occur between September 1, 2015 and August 31, 2016. Subjects will be required to provide legal proof of age. Subjects must be healthy and without contraindications to COC and PHEN. Subjects must also report recent use of COC and must meet diagnostic criteria for COC abuse or dependence using the Structured Clinical Interview for DSM-IV (SCID). Subjects must provide a COC positive urine during screening to verify COC use status. Screening procedures for all subjects will include a medical history questionnaire, laboratory chemistries (blood chemistry screen, complete blood count, ECG and urinalysis) and a brief psychiatric examination. These procedures will be conducted under our lab's screening protocol (03-0509). Chemistry values and screening outcomes must be deemed normal. If chemistry values or screening outcomes fall outside normal ranges, a study physician must deem them clinically insignificant for a subject to be enrolled. An electrocardiogram must also be within normal limits. Any potential subject with a history of serious physical disease, current physical disease, impaired cardiovascular functioning, chronic obstructive pulmonary disease, history of seizure or current or past histories of serious psychiatric disorder that in the opinion of the study physician would interfere with study participation will be excluded from participation. Subjects with current or past histories of substance abuse or dependence that are deemed by the doctor to interfere with study completion will also be excluded from participation. Female subjects must be using an effective form of birth control (e.g., birth control pills, surgical sterilization, IUD, cervical cap with a spermicide, condoms or abstinence) in order to participate. A urine pregnancy test will be conducted before the start of each experimental session to ensure that female subjects do not continue in the study if pregnant. All study subjects will be judged by the study physician, [name] or [name], M.D. to be healthy.

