This experiment will consist of 1 practice session and 8 experimental sessions conducted according to the timeline in Table 1 (see above). After admission, subjects will be allowed to acclimate to the CRIU for two days before beginning the study. During this time, subjects will be maintained on a caffeine-free diet, receive instructions concerning the details of the daily research procedures and general rules of the inpatient research unit and complete a "practice" session to familiarize them with the experimental routine and tasks.

Each day after the practice session, subjects will be awakened at 0700 hours and will receive maintenance medication. Medications will not be administered if a subject's heart rate is  $\geq 100$  bpm, systolic pressure is  $\geq 150$  mmHg or diastolic pressure is  $\geq 100$  mmHg. In addition, the UKU side effects scale will be completed daily to monitor for the emergence of side effects.

Subjects will then be allowed to eat a standard, fat-free breakfast (cereal with skim milk, 2 pieces of toast with jam or jelly and 8 ounces of fruit juice). Tables 2 and 3 (below) outline the activities of maintenance and experimental sessions. The sampling of each session will begin at 0900 hours and will last approximately 1 hour. Self-administration phases will begin at 1330 hours and will last approximately 2 hours. Experimental measures will be completed as outlined in Tables 2 and 3 below. Medications will not be administered if a subject's heart rate is  $\geq 100$  bpm, systolic pressure is  $\geq 150$  mmHg or diastolic pressure is  $\geq 100$  mmHg or if clinically significant and/or prolonged ECG abnormalities are detected.

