Subjects will be excluded from further research participation if at any time during the experimental sessions COC increases heart rate above 130 bpm, systolic pressure above 180 mmHg, diastolic pressure above 120 mmHg or if clinically significant and/or prolonged ECG abnormalities are noted. Subjects will remain seated for the duration of the experimental session. Between the sampling and self-administration phases, subjects will be allowed to eat a standard hospital lunch but will not be allowed to smoke. No experimental activities will be scheduled for the remainder of the day after a self-administration session, but subjects will receive their appropriate maintenance medication at 1900 hours. Subjects will be free to engage in recreational activities (e.g., watch television, read, listen to music, arts and crafts, play video or board games). Research subjects will be required to be in bed with the lights out by 2300 hours.

Time	Table 2-Daily Activities for Maintenance Days
0700	Patient awakened. Vital signs recorded. Medication administered if vitals are within range and no indication of sedation or withdrawal. Subject eats breakfast.
1200	Lunch is served.
1300	UKU completed.
1900	Dinner is served. Vital signs recorded. Medication administered if vitals are within range and no indication of sedation or withdrawal.
2300	Lights out.

Time	Table 3-Daily Activities for Experimental Days
0700	Patient awakened. Vital signs recorded. Medication administered if vitals are within range and no indication of sedation or withdrawal. Subject eats breakfast.
0900	Vital signs recorded. Computerized tasks completed. ECG monitoring begins.
0930	Vital signs recorded. 0 [placebo], 20, 40 or 80 mg intranasal COC administered if vitals are within range. Measures completed 0, 15, 30, 45 and 60 minutes after drug administration.
1030	Sampling phase ends.
1200	Lunch is served.
1300	UKU is completed.
1330	Vital signs recorded. Computerized tasks completed (including progressive-ratio task). ECG

	monitoring begins.
1430	Vital signs recorded. Portion of intranasal dose earned is administered if vitals are within range. Measures completed 0, 15, 30, 45 and 60 minutes after drug administration
1530	Session ends. Remainder of daily activities identical to those listed in Table 2.

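### Does the tolerability hypothesis need a written comparison of removals, withheld doses, adverse events and UKU scores by PHEN condition?

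*Combined protocol and SAP*

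**What the plan says.** Section 1 (Background) gives the hypothesis, "We also hypothesize that COC will be well tolerated during active PHEN maintenance", and the purpose of the session monitoring: "In order to monitor the safety of the drug combinations, cardiovascular measures will be taken routinely throughout experimental sessions". Section 2 (Objectives) makes the reinforcing effects of cocaine the primary objective. The other measures serve to characterise PHEN's influence, and no separate tolerability endpoint is set.

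Section 7 (Research Procedures) supplies the conduct rules:
- a daily scale: "the UKU side effects scale will be completed daily to monitor for the emergence of side effects";
- a hold rule that begins "Medications will not be administered if a subject's heart rate is" and gives limits for heart rate and blood pressure;
- a removal rule: "Subjects will be excluded from further research participation if at any time during the experimental sessions COC increases heart rate above 130 bpm", with parallel limits for blood pressure and ECG.

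Data Analysis, in the same section, plans one set of safety-related comparisons: "Peak-effect and AUC data for the cardiovascular, performance and subjective effects measures obtained during the sampling phase will be analyzed in a similar fashion". It then sets aside the afternoon data: "Cardiovascular, performance and subjective effects data from the self-administration phase will not be analyzed". The reason given is that intake in that phase will vary between subjects. Section 4 (Study Population) sets the recruitment target: "We intend to enroll thirty six (24 male and 12 female) completers into the study". Section 17 requires all adverse events to be collected, documented, reviewed weekly and followed to resolution.

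**The concern.** A hypothesis about tolerability suggests an analysis to go with it, and section 9 (Potential Risks) itself warns that side effects may be more frequent and larger with the combination. Yet the plan's most direct markers of poor tolerance (removals, withheld doses, adverse events and UKU scores) appear only as monitoring. The removal rule covers both session phases, so a subject could be removed after the 1430 dose without that event entering any planned analysis.

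The recruitment target refers to completers. If the analysis were also restricted to completers, it would contain no removals in either condition by construction. The subjects who reacted most would leave the comparison, and PHEN's cardiovascular effect would be understated. A conclusion of good tolerability could then rest on a selected group.

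**Working it through.** The plan gives no numerical criterion or power figure for tolerability. Its one design calculation (36 subjects, d = 0.44, power 0.80) concerns reinforcing effects, so there is no stated figure to reproduce.

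**1. What the planned analyses leave out.**
- *Side effects.* Section 9 lists 18 common side effects. Nine are matched by an Appendix A item, the DSST or the cardiovascular measures: nervousness, restlessness, faintness (taken as dizziness), irritability, shaking, nausea, sweating, performance impairment, and heart rate or blood pressure change. Nine have no specific item: headache, flushing, increased urine production, rash, blurred vision, nose or throat irritation, difficulty sleeping, loss of appetite, weight change. So 18 − 9 = 9 are seen only through UKU, adverse events or the general bad-effects item.
- *Days.* Table 1 has maintenance on days 3–32, which is 30 days. Sessions fall on days 14–17 and 29–32, which is 4 + 4 = 8 days.
- *Readings.* Table 3 gives 5 post-dose times in each of 2 phases: 8 × 2 × 5 = 80 per completer. Of these, 8 × 5 = 40 belong to self-administration and are not analysed.

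**2. What they retain.** The 40 sampling readings follow the full cocaine dose under each PHEN condition. The afternoon dose is at most 10 × 1/10 = 1 sampled dose, and it varies with the subject's choices. The retained half is therefore the half with fixed exposure, and its comparison by PHEN is planned. On session days UKU is completed at 1300. That is before the 1430 dose but 3.5 hours after the full 0930 dose, and the scale is repeated daily.

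**3. Whether removed subjects are dropped.** In section 4, completers is a recruitment target. Section 7 names a mixed-model ANOVA, and section 17 names SPSS. Depending on the procedure chosen, partial records can be kept or lost. No section says that removed subjects are excluded from analysis.

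**4. Size if they were dropped.** The documents give no heart-rate distribution, so every input here is assumed: mean placebo peak 95 bpm, SD 14, true PHEN effect 8 bpm, within-subject correlation 0.3–0.8, and removal at the first sampling-phase peak above 130 bpm. With 95 bpm as the average over the four cocaine doses, completers-only analysis understates the PHEN effect as follows.

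| PHEN effect | Understated by | In bpm (× 8) | Standard error, 36 completers |
|---|---|---|---|
| Constant | 1–5% | 0.1–0.4 | 0.7–1.3 |
| Varies between people (SD 6) | 7–14% | 0.6–1.1 | 1.2–1.6 |

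If 95 bpm is instead the peak at 0 mg cocaine, the understatement is 2–9% (0.2–0.7 bpm) and 10–22% (0.8–1.8 bpm). A 5 bpm shift in one assumed input roughly doubles the number removed, so these figures illustrate the mechanism but do not measure it.

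**5. Whether a prescribed model would repair it.** A mixed model on all available sessions recovers the assumed 8 bpm to within 0.8% when removals are the only loss, but with variances treated as known. Once pre-dose holds are also simulated, it understates by 4–6% (constant effect) or 7–9% (varying effect), against 3–8% and 8–15% for completers. At correlation 0.8 with a constant effect it is no better than completers.

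**6. What a formal comparison of removals could show.** With an exact two-sided McNemar test, 5 discordant subjects all in one direction give 2 × 0.5⁵ = 0.0625, and 6 give 2 × 0.5⁶ = 0.031. At least 6 are needed. With 36 pairs, power is 0.15 if 10% have the event on PHEN only and none on placebo only. With 0 events in 36, the two-sided 95% upper limit is 1 − 0.025^(1/36) = 9.7%. A subject removed in the first period also never supplies a pair. Only descriptive counts are realistic.

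**The case for a change.** The strongest case for a change is that the hypothesis is explicit, UKU is the daily side-effect instrument, and neither it nor the removals have a planned analysis. Varying intake is a sound reason not to compare afternoon means, but it does not prevent counting breaches. Weekly review of adverse events is not a comparison with placebo. The data exist, so writing down a table and an analysis set would cost little.

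Much of this is correct. The omissions are as described, and the counts in steps 1 and 2 are right. What does not stand is the step from omission to harm. The hypothesis says that cocaine will be well tolerated on PHEN; it does not say as well tolerated as on placebo, so no stated objective turns on a between-condition test of these events. The explicit rule about afternoon data is reasonable for its purpose and does not forbid reporting removals. Removals and withheld doses follow from limits the plan sets out, and adverse events must be documented, so the information survives whatever model is fitted. The selection argument depends on an exclusion the plan never states.

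**Conclusion.** No change to the plan is needed. This is missing reporting detail that analysts normally fill: subject disposition with reasons, and side effects by maintenance condition. The cardiovascular, performance and subjective comparisons most relevant to tolerability, at the full fixed dose, are already planned. The documents show no bias. Under assumed inputs the cost of a completers-only analysis is 0.1–1.1 bpm of an 8 bpm effect, or up to about 1.8 bpm on the less favourable reading, and the primary efficacy analysis is not in question.

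This rests on two assumptions: that recorded removals, holds and adverse events are reported alongside the sampling-phase results, and that completers describes recruitment and not an analysis set. If a report claimed good tolerability from completers alone and did not account for those removed, that would be a fault in the report.
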